5.2.2.3 Phase II

Progression-free survival (PFS) based on central review

The rules are the same as the ones described in Section 5.1.3, except the rule defined below. Instead of investigator assessment, the assessment based on central review will be used.

It should be referred to the imaging charter for more details regarding the assessment of response. However, there is one important change to RECIST 1.1 in the assessment of target lesions based on central review. In case one patient has the following:

- PR at last assessment
- more than 20% increase from nadir in the sum of longest diameters of target lesions, but less than 5 mm absolute increase from nadir.

In this case the assessment of PR should be carried forward to PR. This difference will not affect the endpoint PFS of this trial.

Overall survival (OS)

OS is defined as the time from randomisation until death from any cause.

For patients with 'event' as an outcome for overall survival:

• Overall survival [days] = date of outcome – date of randomisation + 1.

For patients with 'censored' as an outcome for overall survival:

• Overall survival (censored) [days] = date of outcome – date of randomisation + 1

The censoring rules for OS (i.e. outcome and date of outcome) are given in Table 5.2.2:3: 1.

Table 5.2.2.3: 1 Derivation rules for OS

Status at time of analysis	Outcome (event or censored)	Date of outcome
Patient died and the date of death is known	event	Date of death
Patient died and date of death is unknown	event	Date of last contact when the patient is known to be alive + 1 day
Patient alive	censored	Date of last contact when the patient is known to be alive
Unknown	censored	Date of last contact when the patient is known to be alive

The date when the patient was last known to be alive will be derived using the following data sources:

- Patient status: date of patient status obtained (if patient status is alive), last date patient known to be alive (in case patient is lost to follow-up), date of refusal (in case the patient actively refused to be followed up)
- Tumour assessment and/or radiological imaging data (date of imaging target lesions, date of imaging non-target lesions, date of detection of new lesion, date of assessment of bone lesions)
- Trial medication administration pages (including dates of start and end of administration, and termination of trial medication page)
- Onset and/or end dates of Adverse Events (AEs)
- Vital signs and/or physical examination dates
- Dates of subsequent anti-cancer therapy

Imputed AE dates as well as imputed subsequent anti-cancer therapy dates will not be used for the derivation of the last contact date.

Time to PSA progression

For the definition of time to PSA progression, the following rules are used:

- If there is a decline from baseline in PSA before increasing: Time to PSA progression is defined as the time from the date of randomisation until the date where a 25% or greater increase in PSA and an absolute increase of 2 ng/mL (=ug/L, unit collected in the trial) or more from the nadir, is documented (which is confirmed by the next available value occurring at least 3 weeks later) (R13-1642). The date of the progression is the first date where the increase is observed.
- If there is no decline from baseline in PSA: Time to PSA progression is defined as the time from the date of randomisation until the date where a 25% or greater increase in PSA and an absolute increase of 2 ng/mL (=ug/L, unit collected in the trial) or more

from baseline, is documented. However, only values after 12 weeks of therapy (i.e. starting at day 84) are considered. In this case no confirmation is needed. (R13-1642)

The percentage change from nadir/baseline will be calculated as follows:

• 100*(PSA value at assessment - PSA value at nadir/baseline)/ PSA value at nadir/baseline

Derivations below are described in days. However, the endpoint will be presented in months in the statistical tables produced for the CTR.

For patients presenting with PSA progression, time to PSA progression is computed by:

• Time to PSA progression [days] = date of PSA progression - date of randomisation +

For patients not presenting with PSA progression or being lost to follow-up, time to PSA progression (censored) is computed by:

• Time to PSA progression (censored) [days] = date of censoring - date of randomisation + 1.

See Table 5.2.2.3: 2 for more details about time to PSA progression rules and derivation of date of censoring.

Table 5.2.2.3: 2	Derivation rules for time to PSA	progression
------------------	----------------------------------	-------------

Situation	Outcome (event or censored)	Date of PSA progression or censoring
No baseline PSA value	censored	Date of randomisation
No post-baseline PSA value	censored	Date of randomisation
No PSA progression, irrespective of missed assessments	censored	Date of last evaluable PSA value
PSA progression, irrespective of missed assessments	event	Date of PSA progression

In the case when confirmation of progression is needed, the censoring rules are defined irrespective of the duration between the first assessment of progression and the confirmatory assessment which only needs to be the next available assessment more than 3 weeks after the first one. In this case, a patient without confirmation of progression will not be considered a progressor.

Data will be carefully checked in order to detect missing assessments. In case further rules are needed, these will be discussed at a BRPM and added in a revision of the TSAP.

Some particular data patterns may lead to a patient having PSA progression and PSA response at the same timepoint. Data will be carefully checked in order to detect such assessments. In case further rules are needed, these will as well be discussed at a BRPM and added in a revision of the TSAP.

Maximum decline in PSA

The maximum decline in PSA is defined as the change in PSA between the baseline PSA value and the minimum post-baseline PSA value. The change from baseline is defined as:

• Change from baseline in PSA (ng/mL) = PSA value post-baseline - PSA value at baseline.

Maximum decline in PSA is defined as:

• Maximum decline in PSA (ng/mL) = min(PSA value post-baseline) – PSA value at baseline.

Percentage decline will be calculated too (please refer to Section 5.1.2 for the computation). A negative change from baseline in PSA shows a decline in PSA.

Percentage change in PSA at week 12

Percentage change in PSA from baseline to week 12 of treatment is defined as:

• Percentage change in PSA (%) = 100*(PSA value at week 12 - PSA value at baseline)/PSA value at baseline

For this assessment, it is allowed to take a value:

- until one week later than week 12, in case the PSA assessment was delayed
- one day earlier due to the one day window allowed by the protocol

Values from assessments between day 84 and day 92 after first treatment administration will therefore be taken into account (according to the protocol schedule for visits at week 12).

In case there are several values within this timeframe (day 84 to 92), the closest value to Day 85 will be taken.

In case there is no value within this timeframe (day 84 to 92), but the patient discontinued all treatments earlier than day 84, then the End of Treatment (EOT) value should be used. A PSA value will be taken as EOT value if the assessment was performed between the date of discontinuation of the last study medication until 7 days (included) after this date (according to the protocol schedule for the EOT visit (EOTV)).

In case there is no value within this timeframe (day 84 to 92), and the patient did not discontinue all treatments earlier than day 84, no earlier value will be taken as replacement, the assessment will be missing.

PSA response

PSA response is defined as a decline in PSA value >50% (with confirmation at least 3 weeks later) (R13-1642). See Section 5.1.2. for more details.

Changes in CTC response

Changes in CTCs will be evaluated using the following criteria:

- CTC reduction is defined as a decline in CTC value from ≥5 to <5 cells per 7.5mL blood (called "specimen volume" within this section and Section 7.5.2.3) (R14-0865), for at least one post-baseline time-point. Patients with a CTC value <5 cells per 7.5 mL blood at baseline, or with missing baseline value, are not taken into consideration for this endpoint.
- Maximum decline in CTC counts (in number of cells) compared to baseline that occurs at any point after treatment start, defined as the difference (absolute and percentage) between the minimum post-baseline CTC value and the baseline CTC value. Patients with missing baseline value are considered missing for this criterion.
- CTC status at week 12 (≥5 or <5 cells per 7.5mL blood)

Baseline value is the value collected before a patient starts treatment with trial medication. Patients with no post-baseline value are considered as missing for the three criteria.

For the criterion "CTC status at week 12", the nearest assessment to C4V1 (day 85) will be used, with following window:

- A later value, until one week after (day 92), can be used
- An earlier value, after four weeks in trial (day 29), can be used.

In case the patient discontinued the trial before the planned assessment, the EOT assessment will be used for this criterion in case it is the nearest to the target day.

In case it is needed for descriptive tables, multiple entries for one single time point in a patient will be assessed as follows:

- If only one valid value (with acceptable specimen volume or imputable value) is available, this one will be used
- If several valid values are available, the value of the time point will be set as the mean of the available values

Proprietary confidential information © 2017 Boehringer Ingelheim International GmbH or one or more of its affiliated companies

GENERAL ANALYSIS DEFINITIONS

6.1 **TREATMENTS**

Phase I escalation and expansion parts: Patients will be analysed according to the cohort initially assigned. All planned analysis will be presented by this cohort, unless specified otherwise. Handling of patients where cohort assignment has not been followed will be handled on a case-by-case basis, to be agreed at report planning meetings or DBL meeting (but prior to DBL).

Phase II part: For safety analyses, treated patients will be analysed according to the treatment they actually received. For efficacy analyses, the intent-to-treat (ITT) approach will be used, i.e. patients will be analysed according to the treatment group they were randomised to.

For safety summaries data recorded during the REP will be considered as on-treatment. For this trial, the length of the REP is 42 days.

The actual study periods and treatment codes are defined in a document entitled "8-7-othersdtm-trial-arms-trial-elements", which can be found in Data Management and Statistics (DMS) folder, Section 8, within Boehringer Ingelheim Regulatory Documents for Submission (BIRDS).

Patients in phase I expansion part are on continuous enzalutamide treatment before the trial and during the screening period. For these patients, the on-treatment period is considered to start at the first intake of xentuzumab.

IMPORTANT PROTOCOL VIOLATIONS

No per protocol set (PPS) analysis will be performed for this study, hence, no patient will be excluded from the analyses (except those with missing informed consent or not adhering to age limit). However patients with potentially important protocol violations (IPVs) will be documented. The following list of potentially IPVs in Table 6.2: 1 will be used; note that this is a working list and may not be finalised until the final Blinded Report Planning Meeting (BRPM) or DBL meeting (but prior to DBL for the primary analysis). Potentially important protocol violations will be handled according to BI standards (7).

During the study conduct, protocol deviation should be monitored and guidance for improving / teaching the respective sites should be discussed during the study Medical Quality Review Meetings (MQRMs).

Table 6.2: 1 Important protocol violations

Cate	egory/ e	Description	Requirements	Excluded from
A [1]		Entrance criteria not met		
	A1	Diagnosis of trial disease questionable	Inclusion criteria* IN1, IN3, IN4 not met	None

Table 6.2: 1 Important protocol violations (cont.)

Category/ Code		Description	Requirements	Excluded from
	A2	Prohibited baseline condition, diagnosis or treatment	Inclusion criteria* IN5, IN6, IN7 or IN16, IN17, IN18 (phase Ib escalation and phase II only) or IN19, IN20 (phase Ib expansion cohort only) not met	None
			or	
			Exclusion criteria* EX1-EX10 or EX13-EX17 or EX21 or	
			EX18, EX22, EX23 (phase Ib escalation and phase II only) or	
			EX19 (phase Ib expansion cohort only) met	
	A3	Laboratory result indicating inadequate	Inclusion criteria* IN8 to IN15 not met	None
		organ function at screening	or	
		screening	Exclusion criterion* EX12 met	
	A4	Adequate archival tumour tissue not available	Not applicable	None
	A5	Relevant medical history available for patients undergoing tumor biopsy only	Exclusion criterion* EX20 met	None
B [1]		Legal Criteria		
	B1	Informed consent not available / not done	Informed consent date missing	All
	B2	Informed consent too late	Informed consent date was after Screening Visit date	None
	В3	Age limit for patient inclusion not adhered to	Inclusion criteria IN2 not met or, Calculate age given the date of birth and date of informed consent: patients must be ≥ 18 years old	All

Table 6.2: 1 Important protocol violations (cont.)

Category/ Code		Description	Requirements	Excluded from
С		Trial medication and randomisation		
	C1 [2]	Time window violation for procedures performed at screening	Screening imaging earlier than 28 days to first drug intake or later than first drug intake;	None
			Safety labs, ECG performed earlier than 28 days to, or later than first drug intake;	
			Timeframe > 4 days between randomisation and first drug intake.	
	C2 [2]	Trial medication not given according to protocol	Dose reduction scheme not followed (see CTP Section 4.1.4.4);	None
	[-]	4]	Administration of trial medication(s) not compliant.	
			Indicated by medical review (i.e. where Administration of xentuzumab according to the protocol = 'No' and associated comments, or compliance data from Enzalutamide with associated comments)	
			Please note: This excludes the investigational treatment given outside the boundaries specified in the CTP (covered in Category C3)	

Table 6.2: 1 Important protocol violations (cont.)

Category/ Code		Description	Requirements	Excluded from
	C3 [1]	Infusion time for the investigational treatment outside of CTP specific boundaries	Infusion duration of xentuzumab given < 50 minutes or > 200 minutes (Infusion time should be from 60 to 180 minutes, but the thresholds above are accepted).	None
			The exact duration of the infusion should be calculated taking interruptions into account.	
			In case of missing administration times, the violation will not be considered important if administration according to protocol = 'Yes'	
	C4 [2]	Patient assignment not followed	Patients do not receive the initial treatment they were randomised / allocated to	None
	C4.1	Randomisation not followed	This applies only for phase II part of the trial	None
	C4.2	Treatment allocation not followed	This applies for all non-randomized parts of the trial.	None
D [2]		Concomitant medication		
	D1	Prohibited treatment during trial conduct phase	Treatment taken during the treatment period as described in Section 4.2.2.1 of the CTP.	None
E [2]		Missing Data		
	E1	Imaging assessments not done according to CTP instructions	Imaging assessment should be performed at Screening and several time points thereafter (see Section 5.1.2.1 of the CTP, Section 6.7.2 of the TSAP).	None

Table 6.2: 1 Important protocol violations (cont.)

F [2]		Trial Specific protocol violations		
	F1	Other protocol violations affecting patient rights or safety	Manual Protocol Violations (PVs) will be collectively captured.	None

^[1] IPV will be derived automatically

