The exploratory expansion cohort is to be conducted in patients that are already undergoing treatment with enzalutamide and are beginning to show a rise in PSA level according to standard criteria (R13-1642). Patients may not have received prior taxane chemotherapy or abiraterone treatment for inclusion into this part of the study. The results of the expansion cohort will not affect the continuation of the randomised phase II trial. Further data concerning safety, QT assessment and drug-drug interactions will also be collected throughout this cohort.

The phase II trial will be performed according to an open-label, randomised design. Blinding is not considered ethical, or necessary. The determination of radiological disease progression will be assessed by the investigational site and as recommended by modified RECIST 1.1 (R09-0262), and Prostate Cancer Clinical Trials Working Group Criteria (PCWG2) (R13-1642) as per Appendix 10.4 and Section 5.1.2.1, to assess whether a patient should remain on trial. However, an independent central imaging unit will be used to analyse and confirm progression free survival endpoint in the phase II trial in a blinded manner. Internal review by the trial team will also be blinded.

All patients will receive the standard enzalutamide regimen that is registered and recommended by the manufacturer during the phase Ib escalation, expansion cohort, and the phase II randomised trial, regardless of the treatment arm to which they are randomised.

The main objective of the trial is to test and support the hypothesis that BI 836845 will improve clinical outcome when combined with enzalutamide in patients with advanced and/or metastatic CRPC.

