Assessments will be performed at screening, or if valid results are available as part of routine clinical practice and are within 28 days prior to start of study treatment, repeat imaging will not be required. Imaging will be at baseline and then every 2 cycles (8 weeks) up to week 24 and then every 3 cycles (12 weeks) thereafter i.e. prior to the start of cycles 3, 5, 7, 10 onwards. Tumour assessments may be performed up to 7 days prior to the scheduled date for start of the relevant cycle/assessment date.

In the event of a delay, interruption or discontinuation of treatment, tumour assessment should continue to follow the original schedule. The schedule should be followed until progression is observed or until the patient commences further treatment for disease, whichever occurs first. For patients who prematurely discontinue study medication without disease progression, tumour assessments should continue to be performed until disease progression or start of further treatment.

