Further details of the independent review are described in the Imaging Charter. Modifications of the conventional RECIST 1.1 lesion measurement criteria will be introduced into the measurement process in an attempt to reduce variability in the measurements for the independent central imaging review. Eligibility and treatment decisions will be based on the assessment of disease by the investigator (as per Section 5.1.2.1 and appendix 10.4). Central imaging will not be used for this purpose and the results of the central imaging review will not be communicated to the investigator.

5.2 **SAFETY**

5.2.1 **Endpoint(s) of safety**

Safety of BI 836845 when administered together with enzalutamide will be evaluated by intensity and incidence of AEs, and will be graded according to National Cancer Institute (NCI) Common Terminology Criteria for Adverse Events (CTCAE) Version 4.03 dated 14 June 2010 (R10-4848). Safety endpoints will include:

BI Trial No.: 1280.8 Doc. No.: c02304008-15

2. No.: c02304008-15 Trial Protocol Version 12 Page 64 of 241

Proprietary confidential information. © 2022 Boehringer Ingelheim International GmbH or one or more of its affiliated companies. All rights reserved.

Primary endpoints (Phase Ib Escalation):

- Number of patients with Dose Limiting Toxicities
- Maximum Tolerated Dose (MTD) of BI 836845

All other safety endpoints will be defined in Section 5.3.1 and details are provided in Section 5.2.2.

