7.3.2 Secondary analyses

The analysis of PFS based on independent review data will be performed in the same way as the primary evaluation on investigator assessments.

Overall survival will be analysed using a Cox proportional hazards model in the same way as the primary endpoint for phase II (see Section 7.3.1). A hazard ratio and 95% confidence interval for BI 836845 in combination with enzalutamide vs. enzalutamide alone will be presented. Kaplan-Meier estimates of overall survival will be plotted by treatment group. A log-rank test will also be performed to compare the survival curves.

The first analysis of overall survival will be performed at the time of primary PFS analysis. The analysis will be updated once all patients have completed the last follow-up visit and/or when an adequate number of patients have died. The time to PSA progression will be analysed using a Cox proportional hazards model in the same way as the primary endpoint for phase II (see Section 7.3.1). In addition, the percentage change from baseline in PSA will be summarized descriptively. The maximum decline in PSA compared to baseline will be explored graphically. Further details will be provided in the TSAP.

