Due to the inherent difficulties determining radiographic progression in this indication, a central imaging unit is employed to interpret the radiographic images and obtain an independent tumour assessment in addition to the investigator's assessment. However, due to these difficulties, there is potentially a high discordance rate between the independent review and the investigators (fewer independent review events compared to investigator assessed events). From Table 7.6: 2 it can be seen that having a discordance rate of going up to 33% – leaving potentially only 40 independent review events – still gives a probability of between 0.66 and 0.74 (corresponding true underling HR of between 0.65 and 0.70) of observing a HR of less than 0.8 in the evaluation of the independent review as well. If the true underlying HR should be 1.0, then the probability of observing a HR of 0.8 is still sufficiently low with 0.24.

Due to the patients' advanced condition and previous treatment regiments obtained before joining this study, the estimated median PFS time in the enzalutamide arm is around 3 months, and between 4.3-4.6 months in the combination arm of BI 836845 + enzalutamide.

² Calculated based on the approximate normal distribution of the estimated log hazard ratio, i.e. assuming the log hazard ratio is normally distributed with mean log(true hazard ratio), and variance (4 / number of PFS events) (R10-4988).

³ Note that 70 events out of 80 patients can only be seen if the number of permanently censored patients is very low.

Proprietary confidential information. © 2022 Boehringer Ingelheim International GmbH or one or more of its affiliated companies. All rights reserved.

Assuming recruitment rates of 10-13 patients per month for a period of A months, the percentage of observed PFS events relative to sample size is a function of study duration T:

$$\frac{1}{2} \left[\left(1 - \frac{e^{-\lambda_1(T-A)} - e^{-\lambda_1 T}}{A\lambda_1} \right) + \left(1 - \frac{e^{-\lambda_2(T-A)} - e^{-\lambda_2 T}}{A\lambda_2} \right) \right].$$

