Proprietary confidential information © 2017 Boehringer Ingelheim International GmbH or one or more of its affiliated companies

If patients would have their radiological examinations over a number of days, i.e. target lesions assessed on day x, non-target lesions assessed on day y and new lesion (if applicable) on day z, the following rules will be applied:

- If the overall response is PD, the earliest date of multiple assessments will be taken.
- If the overall response is SD, Non-CR/Non-PD, Non PD, PR, CR or NE, the latest of multiple assessment dates will be taken, i.e. in the case of SD, Non-CR/Non-PD, Non PD, PR, CR, the latest of multiple dates will be used to censor the patients.

For PFS according to RECIST and PCWG2, the date of overall response will be determined for RECIST and PCWG2 separately. In case both RECIST and PCWG2 show PD then the date of PD will be the earliest date of these two. When either RECIST or PCWG2 show PD, then the date of outcome will be the date of PD. In case none of RECIST or PCWG2 shows PD then the latest date of RECIST and PCWG2 will be used for censoring.

Imaging assessments for which NE is assigned as the overall response at an imaging time-point are considered to be missed assessments. Please note that NE does not indicate lack of progression.

Table 5.1.3: 1 Derivation rules for PFS

Situation	Outcome (event or censored)	Date of outcome		
No baseline radiological assessment				
Patient with death on or before the second planned radiological assessment	Event	Date of death		
Patient without death or patient with death after second performed radiological assessment	Censored	Date of randomisation (or first treatment administration, in non-randomised trials)		
Without post-baseline radiological assessments				
Vital status is unknown or patient is known to be alive	Censored	Date of randomisation (or first treatment administration, in non-randomised trials)		
Death prior or on the second planned radiological assessment	Event	Date of death		

Table 5.1.3: 1 Derivation rules for PFS (cont.)

Situation	Outcome (event or censored)	Date of outcome
Death beyond the second planned radiological assessment	Censored	Date of randomisation (or first treatment administration, in non-randomised trials)
With baseline and post-batherapy	seline radiological a	ssessments BUT no other anti-cancer
Alive and not progressed, no more than one consecutively missed radiological assessments	Censored	Date of last radiological assessment

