7.5.2.3 Phase II

PFS based on central review

PFS based on central review will be analysed using the same methods as for the primary endpoint for phase II (see Section 7.4.3), including subgroup analyses, if deemed appropriate.

OS

OS will be analysed using the same methods as for the primary endpoint for phase II (see Section 7.4.3), including subgroup analyses, if deemed appropriate.

Time to PSA progression

Time to PSA progression will be analysed using a Cox proportional hazards model in the same way as the primary endpoint for phase II (see Section 7.4.3).

Maximum decline in PSA

Descriptive statistics for maximum decline in PSA will be displayed. This endpoint will also be explored graphically by means of a waterfall plot (using the percentage decline). All PSA assessments will be displayed in a longitudinal plot.

Percentage change in PSA at week 12

Descriptive statistics for percentage change in PSA at week 12 will be provided. This endpoint will also be explored graphically by means of a waterfall plot. All percentage changes in PSA will be displayed in a longitudinal plot.

PSA response

Descriptive statistics for PSA response will be provided. Confirmed as well as unconfirmed responses will be displayed.

Changes in CTC response

Imputations as specified in Sections 5.2.2 and 7.5.2.2 will be performed before the analysis, separately for each sample.

Frequencies of patients with CTC reduction will be displayed.

The maximum decline (percentage) in CTC counts compared to baseline will be analyzed descriptively and also explored graphically by means of a waterfall plot. All CTC assessments will be displayed in an overtime plot per patient.

Difference in proportions for week 12 status will be displayed by means of a contingency table, along with 95% confidence interval and a Fisher's exact test.

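### Central-review PFS censors many unconfirmed investigator progressions at the last scan, so its hazard ratio supports the primary result only if non-confirmation is similar in the two arms

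*SAP*

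**What the plan says.** **Role.** PFS by central review is a secondary endpoint of phase II. Protocol 3.2 gives it a specific task: "an independent central imaging unit will be used to analyse and confirm progression free survival endpoint in the phase II trial in a blinded manner".

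**Rules and methods.** SAP 5.2.2.3 applies the derivation rules of SAP 5.1.3 to the central reads: "Instead of investigator assessment, the assessment based on central review will be used". Protocol 7.3.2 agrees: "The analysis of PFS based on independent review data will be performed in the same way as the primary evaluation on investigator assessments". So does SAP 7.5.2.3: "PFS based on central review will be analysed using the same methods as for the primary endpoint for phase II".

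**When imaging stops.** Protocol 5.1.2.1: "The schedule should be followed until progression is observed or until the patient commences further treatment for disease, whichever occurs first". Treatment decisions rest on the investigator's reading. On the central reads, Protocol 5.1.3 (Central Imaging) says: "Central imaging will not be used for this purpose and the results of the central imaging review will not be communicated to the investigator".

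**Censoring.** In SAP Table 5.1.3:1, the row "Alive and not progressed, no more than one consecutively missed radiological assessments" censors at the last radiological assessment. A patient who starts new anti-cancer therapy before progression or death is censored at the last assessment before that therapy.

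**Expected discordance.** Protocol 7.6 anticipates the shortfall: "there is potentially a high discordance rate between the independent review and the investigators (fewer independent review events compared to investigator assessed events". It allows for discordance of up to 33%, so that 60 investigator events leave 40 central events. It then gives the probability of an observed HR below 0.8 as 0.66 to 0.74 for true HRs of 0.70 to 0.65, and 0.24 for a true HR of 1.0.

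**The concern.** Take a patient whom the investigator calls progressed and central review does not. The investigator's call normally ends the scan schedule, and the site never learns of the disagreement. No later scan then exists on which central review could find progression, and the table censors the patient at the last scan. That is the moment at which a physician who had seen the patient judged the disease to be advancing, so the censoring is related to the outcome.

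Protocol 7.6 treats the loss only as fewer events. Its formula widens the variance and leaves the mean at the true log HR. That is right if non-confirmation is equally frequent in the two arms. Investigators know the treatment here, and nothing in the documents secures that equality.

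What is at stake is interpretation. Protocol 7.2 bases inference on the size of the observed PFS difference rather than on formal testing, and Protocol 2.1 says that the data will feed phase III assumptions. Central review is the blinded check on an open-label primary endpoint. If its medians or HR are distorted, agreement or disagreement with the primary result is hard to read.

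**Working it through.** **1. The plan's figures.** Footnote 2 of Protocol Table 7.6:2 treats the log HR as normal with variance 4/events, so P(observed HR ≤ 0.8) = Φ[ln(0.8/HR) / √(4/events)]. With 60 × (1 − 1/3) = 40 events, √(4/40) = 0.316.

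- HR 0.65: 0.208/0.316 = 0.66, probability 0.744 (stated 0.74)
- HR 0.70: 0.134/0.316 = 0.42, probability 0.664 (stated 0.66)
- HR 1.0: −0.223/0.316 = −0.71, probability 0.240 (stated 0.24)

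All reproduce. The 60-event figures (0.79, 0.70, 0.19) do too.

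**2. Effect on the HR.** Suppose a share d of investigator progressions is unconfirmed, independently of time, and is censored at that point. The central hazard in that arm is then (1 − d) times the investigator hazard, and

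central HR = true HR × (1 − dA)/(1 − dB).

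The documents give no split by arm. The splits below are assumptions that average 33%.

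| dA | dB | Factor | True HR | Central HR | P(HR ≤ 0.8), 40 events |
|---|---|---|---|---|---|
| 33% | 33% | 1.00 | 0.65 | 0.65 | 0.74 |
| 33% | 33% | 1.00 | 1.0 | 1.0 | 0.24 |
| 28% | 38% | 1.16 | 0.65 | 0.755 | 0.57 |
| 38% | 28% | 0.86 | 1.0 | 0.86 | 0.41 |
| 23% | 43% | 1.35 | 0.65 | 0.88 | 0.38 |
| 43% | 23% | 0.74 | 1.0 | 0.74 | 0.60 |

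For example, 0.72/0.62 = 1.161 and 0.65 × 1.161 = 0.755; conversely 0.62/0.72 = 0.861.

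A simulation (40 per arm, Cox model with Breslow ties, 1,000 runs per scenario, continuous event times) agrees. With equal discordance the central and investigator HRs were 0.644 and 0.642 under an effect, and 1.010 and 1.006 under none. At 23%/43% the HR moved from 0.64 to 0.87. At 43%/23% under no effect it moved from 1.00 to 0.74.

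**3. Effect on medians, equal discordance of one third.** From the medians of 3 and 4.6 months in Protocol 7.6, the central medians become 3/(2/3) = 4.5 and 4.6/(2/3) = 6.9 months, a gap of 2.4 months. What continued imaging would have shown depends on the delay to central progression, which the documents do not give.

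- *Continuous event times:* a mean delay of 8 weeks gives 3.7 and 5.3 months. Mean delays of 4, 8, 16 and 24 weeks give gaps of 1.6, 1.6, 1.8 and 1.9 months, all below 2.4.
- *Events seen only at the protocol's scans* (weeks 8, 16, 24, then every 12): an 8-week delay gives a planned gap of 2.8 against 1.8 months. At 16 or 26 weeks the two sets of medians coincide at 5.5 and 8.3 months.

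The tendency is towards longer medians, but no single percentage can be attached to it.

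**The case against.** Several points on the other side stand.

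- **Equal discordance leaves the HR alone.** The protocol's probabilities are then correct as printed, and no stated figure is wrong.
- **The splits by arm are assumed.** Nothing in the documents points to a difference of 10 or 20 percentage points, or to its direction.
- **The 33% is easily misread.** A reader might infer that one third of investigator progressions will go unconfirmed and be censored. Protocol 7.6 gives an upper planning bound on the net shortfall in PFS events, and PFS events include deaths.
- **Not every unconfirmed case is lost.** A death with at most one missed assessment and no new therapy remains an event (SAP Table 5.1.3:1). New bone lesions inside the 12-week flare window need a second scan at least 6 weeks later, and a repeat scan is recommended for marginal or equivocal progression at the first RECIST assessment (Protocol 5.1.2.1). An end-of-treatment scan is due unless one was done within 4 weeks (Protocol flow chart). These reduce the problem without removing it.
- **Absence cannot be proved.** The imaging charter and some SAP sections (5.3, 5.4, 6.4 and 7.6, for instance) are not visible here. SAP 7.5.2.3 refers to subgroup analyses that the readable text of SAP 7.4.3 does not contain, so relevant text may be missing.
- **Central PFS is secondary in an exploratory trial.** No error rate is at risk.

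The condition written into Protocol 7.6 is a separate matter. That text is fully visible and does not say that its probabilities assume equal discordance.

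**Conclusion.** The mechanism follows from the documents: investigator-PFS censoring rules, imaging that normally ends on the investigator's call, and no feedback of central results. Central medians will tend to be too long, by an amount that depends on an unknown delay. The central HR is unbiased only if non-confirmation is similar in the two arms. Under the assumed 10-point differences, a true 0.65 reads as 0.755 or a true 1.0 as 0.86, and the bias could go either way.

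A reader might conclude that central review cannot serve as confirmation at all. The documents do not support that, because with similar discordance in the arms the HR and the plan's probabilities are unaffected. The supportable conclusion is narrower: the central HR should not be read as confirming the primary result until discordance has been shown by arm. The primary analysis is untouched. The change is worth making because it is cheap.

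**What to change.** Unless SAP text not visible here already covers it:

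1. In SAP 7.5.2.3, report the discordance between investigator and central progression by arm, separating early discrepancies (investigator before central, or never confirmed) from late ones (central before investigator).
2. Add a supportive sensitivity analysis of central PFS that counts as an event, at that scan, any investigator progression that ended imaging without central progression. Show its HR and medians beside the planned central analysis.
3. In Protocol 7.6, state that 0.66 to 0.74 and 0.24 assume equal discordance in the two arms.

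The cost is some wording, one table and one re-run of the Cox and Kaplan-Meier programs on data already held; no extra scans or readers are needed. The sensitivity analysis brings unblinded investigator calls back into a blinded endpoint, so it is supportive only and does not replace the planned central analysis.
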